5.15.1.3. Tissue Factor Pathway Inhibitor (TFPI)

For patients enrolled under Amendment 4, TFPI will be collected at baseline (i.e., prior to and and an anterest treatment), EOI, 4, 8, 12, 24, 48, and 72 hours, and 7 days post and an anterest treatment. TFPI Activity, Free TFPI antigen, and Total TFPI antigen will be determined.

Mean, median, standard deviation, minimum, and maximum value, and 95% CI for the median will be presented for each time. Confidence intervals will be estimated using a distribution free procedure as described above for the primary efficacy analysis.

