11.7.4. Laboratory Parameters

Clinical laboratory parameters including hematology, chemistry, and coagulation markers (e.g., anti-fXa activity and thrombin generation) will be summarized by time point.

Baseline values, the values at each subsequent visit, and changes from baseline will be summarized for each of the quantitative laboratory assessments.

Shift tables of chemistry, hematology, and coagulation markers will be used to summarize change from baseline to post-baseline time points.

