Appendix G: Examples of Minor Procedures Allowed

Appendix H: National Institutes of Health Stroke Scale (NIHSS)

Appendix I: Protocol Summary of Changes (Amendment 5 vs Amendment 6)

APPENDIX A. SCHEDULE OF ACTIVITIES

Study Day	1									2		3	$30^{[12]}$	
	-3:00	-00:15	00:00 to	EOB t (120 r		EI + 1 hr	EI + 4 hrs	EI + 8 hrs	EI +	EI + 18 hrs	EI + 24 hrs	EI + 48 hrs	EI + 72 hrs	
Study Hour and Time Window	to -00:01	to -00:01	EOB (15-30 min)	EOB +30 min	EI -30 min	+/- 30 min	+/- 30 min	+/- 90 min	+/- 1 hour	+/- 1 hour	+/- 1 hour	+/- 2 hour	+/- 6 hour	+7 d
Obtain Consent [1]	X													
Determine Eligibility	X													
Obtain Medical History [2]	X													
Obtain Prior Medications [2][13]	X													
Weight [3]	X													
Vital Signs (BP, HR, RR, temp)	X	X		X	X	X	X	X	X					
Local Labs: INR	X													
Local Labs: Chemistry & pregnancy test [4]	X													
Local Labs: CBC		X							X					
Critical Efficacy Central Labs: Anti-fXa activity unbound anticoagulant		[9] [14] X		[9] [14] X	[9] [14] X		X	X	X					
Critical Efficacy Central Labs: Thrombin Generation	X			X [11]	X [11]		X	X	X	X	X	X	X	X
Critical Immunogenicity Central Labs: Antibodies to andexanet, FX, FXa nAb (andexanet) nAb (FX/FXa)	X													X
Exploratory Efficacy Central Labs: TFPI Panel & ATIII	X				X		X	X	X		X	X	X	X

Study Day	1			1						2	3	3	30 ^[12]	
Study Hour and Time Window	-3:00 to -00:01	-00:15 to -00:01	00:00 to EOB (15-30 min)	EOB t (120 n EOB +30 min		EI + 1 hr +/- 30 min	EI + 4 hrs +/- 30 min	EI + 8 hrs +/- 90 min	EI + 12 hrs +/- 1 hour	EI + 18 hrs +/- 1 hour	EI + 24 hrs +/- 1 hour	EI + 48 hrs +/- 2 hour	EI + 72 hrs +/- 6 hour	+7 d
Administer and exanct bolus, immediately followed by an infusion			Bolus	Infus	ion									
Echocardiogram Pericardial Bleeds	X								X					
CT or MRI (e.g., ICH and intra-spinal) [5]	X [10]					X			X					X
Glasgow Coma score (ICH patients only)	X					X			X					X
Modified Rankin score (ICH patients only)	X					X			X					X
NIH Stroke Scale (ICH patients only) (Appendix H)		X				X			X					X
Record blood products and hemostatic treatments [6]		X												
Record bleeding-related diagnostic and therapeutic procedures [7]		X												
Record volume of colloid and crystalloid [6]			X											

Study Day		1					2	3	3	30 ^[12]				

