2.3. Exploratory Efficacy Objectives

- For patients receiving apixaban, rivaroxaban, or edoxaban, to evaluate the decrease in the free fraction of the FXa inhibitor following andexanet treatment.
- To evaluate the effect of andexanet on thrombin generation.
- To evaluate the effect of andexanet on levels of tissue factor pathway inhibitor (TFPI).
- To evaluate the effect of and examet on levels of antithrombin III (ATIII).
- To evaluate the effect of andexanet on anti-factor IIa levels for patients receiving enoxaparin.
- To evaluate hemostatic efficacy in intracranial hemorrhage (ICH) patients at high risk for hematoma expansion.
- To evaluate the use of red blood cell transfusions.
- To evaluate the use of other blood products and hemostatic agents.
- To evaluate the occurrence of adjudicated re-bleeding in patients following andexanet treatment. Re-bleeding is defined as follows: recurrent bleeding from the same or another anatomical site, or new bleeding from a different anatomical site in patients within 24 hours of initial andexanet treatment and after achieving initial good/excellent hemostasis. For patients with ICH, to evaluate change in clinical status following andexanet treatment.

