5.15.1.1. Free Fraction of the FXa Inhibitor

The Free Fraction Plasma Concentration (ng/mL; also known as unbound plasma fraction) of apixaban, rivaroxaban, and edoxaban will be evaluated at Baseline (prior to andexanet treatment), and at EOB, EOI, 4, 8, and 12 hours after the end of andexanet infusion. In addition, % Protein Binding will be determined.

Change and percent change from baseline in Free Fraction of the inhibitor to the minimum value during and and an administration (i.e., minimum value between (EOB and EOI), and to each time point will be calculated. Mean, median, standard deviation, minimum, and maximum value, and 95% CI for the median will be presented. Confidence interval will be estimated using distribution free procedure as described above for primary efficacy analysis. In addition, the time course of unbound inhibitor concentrations following and an analysis will be presented. Protein Binding will be presented as listings.

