5.15.1.4. Antithrombin III (ATIII)

For patients enrolled in Amendment 4, ATIII will be collected at baseline prior to and exanet treatment, EOI, 4, 8, 12, 24, 48, and 72 hours, and 7 days post and exanet treatment. Mean, median, standard deviation, minimum, and maximum value, and 95% CI for the median will be presented. Confidence intervals will be estimated using a distribution free procedure as described above for the primary efficacy analysis.

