5.15.1.5. Anti-Factor IIa Activity

For enoxaparin patients, Anti-factor IIa levels (pre- and post-administration of andexanet will be collected. Outcome will be presented in a summary table for each time point and data listing by patient.

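### For TFPI, ATIII and anti-IIa the SAP summarises levels only, with no within-patient change from baseline, and for TFPI and ATIII it names a 7-day sample where the schedule has Day 30

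*SAP*

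**What the plan says.** SAP 2.3 frames the exploratory objectives as effects (for TFPI: "To evaluate the effect of andexanet on levels of tissue factor pathway inhibitor (TFPI"), with parallel wording for ATIII and anti-IIa. Protocol 11.5.4 defines the matching endpoints as levels before and after andexanet.

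The planned analyses are these:

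- **TFPI (SAP 5.15.1.3):** location and spread of the level, and "95% CI for the median will be presented for each time".
- **ATIII (SAP 5.15.1.4):** "Mean, median, standard deviation, minimum, and maximum value, and 95% CI for the median will be presented". That the summary is repeated at each time is not written here, but the listed ATIII table is an over-time table.
- **Anti-IIa (SAP 5.15.1.5):** "Outcome will be presented in a summary table for each time point and data listing by patient".

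The neighbouring sections differ. For free fraction, SAP 5.15.1.1 plans "Change and percent change from baseline in Free Fraction of the inhibitor to the minimum value" and also to each time point. SAP 5.15.1.2 does the same kind of thing for ETP. Protocol 11.7.4 says that baseline values, later values and "changes from baseline will be summarized for each of the quantitative laboratory assessments".

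On timing, SAP 4.5.2, 4.5.4, 5.15.1.3 and 5.15.1.4 list baseline and then "EOI, 4, 8, 12, 24, 48, and 72 hours, and 7 days post" treatment. The schedule row in protocol Appendix A, labelled "Exploratory Efficacy Central Labs: TFPI Panel & ATIII", has no 7-day visit. Its last sample is at Day 30, with a window of Days 30 to 37.

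**The concern.** With no control arm, the natural estimate of an effect on a laboratory level is the change within each patient from the pre-dose sample. A table of levels at each time does not give it. The reader has to set the baseline row against a later row, without the benefit of the pairing and possibly with different patients in the two rows, because those who die or miss a sample leave the later row but stay in the baseline one.

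TFPI has a stated scientific purpose. Protocol 3.4.3 suggests that TFPI inhibition may help to maintain hemostasis for 10 to 20 hours after andexanet has largely cleared, and says that TFPI antigen was added for that reason. SAP 4.5.2 also uses TFPI in the safety analysis. At stake are the precision and clarity of that exploratory evidence and, at Day 30, whether the last scheduled sample is reported under its correct time.

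**Working it through.** The documents give no SD, effect size or within-patient correlation for these assays, so there is no figure of the plan's to reproduce. The check is mainly a comparison of sections.

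**Step 1. Which laboratory endpoints get a change from baseline in the SAP?**

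| Endpoint | Definition | Analysis | Change planned? |
|---|---|---|---|
| Free fraction | 4.5.1 | 5.15.1.1 | Yes, to the on-treatment minimum and each time |
| ETP | 4.5.3 | 5.15.1.2 | Yes, to peak and each time |
| TFPI | 4.5.2 | 5.15.1.3 | No; levels with a median CI |
| ATIII | 4.5.4 | 5.15.1.4 | No; levels with a median CI |
| Anti-IIa | 4.5.5 | 5.15.1.5 | No; by-time table and listing, no CI |

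**Step 2. Is it supplied elsewhere?** Protocol 10.2.3 lists TFPI, ATIII and anti-IIa under clinical laboratory testing, so protocol 11.7.4 can be read as covering them. The SAP does not take that up. Its laboratory section, 5.16.6, plans changes from baseline only for hematology at 12 hours, plus normal-range shift tables. SAP 5.9 already restricts any change table to patients with both a baseline and a follow-up value, so the rule for forming pairs exists. For these three assays there is no change table to apply it to.

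**Step 3. What can be recovered from the level tables?** The median of the within-patient changes is in general not the difference of the two medians, so it cannot be read off. With complete pairs the difference of the two means does equal the mean change, but its standard error cannot be recovered without the correlation.

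Let s be the SD at both times (assumed equal), n the number of patients and rho the correlation between a patient's two values:

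- unpaired SE of the difference = s × sqrt(2/n)
- paired SE of the mean change = s × sqrt(2(1 − rho)/n)
- ratio, paired to unpaired = sqrt(1 − rho)

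Rho is not in the documents. Over an assumed range:

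- rho 0.3: sqrt(0.7) = 0.84
- rho 0.5: sqrt(0.5) = 0.71
- rho 0.7: sqrt(0.3) = 0.55

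These ratios are for means. The SAP's CI is for a median, so they are a guide to the gain and not its exact size.

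**Step 4. Sampling times for TFPI and ATIII, side by side.**

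- SAP: baseline, EOI, 4, 8, 12, 24, 48 and 72 hours, 7 days (nine times).
- Appendix A: pre-dose, end of infusion, 4, 8, 12, 24, 48 and 72 hours, Day 30 (nine times).

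Eight agree and the last does not. For thrombin generation, SAP 4.5.3 and 5.15.1.2 do list Day 30, as Appendix A does. The Day 30 column in Appendix A carries a +7 day window, which is a likely source of the 7-day entry, though that is inference.

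**The case against.** The strongest reply is that the SAP follows the endpoints as worded. Protocol 11.5.4 uses change from baseline for GCS, mRS and NIHSS and a decrease for free fraction, but only levels before and after treatment for these three assays. Protocol 10.1.6 and 10.1.7 present TFPI and ATIII as context for the state of coagulation. No hypothesis, threshold or decision rule is attached to them. This stands, and it limits the point to better reporting of exploratory endpoints.

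Second, protocol 11.7.4 already promises changes from baseline. This also stands. A reader might infer that the trial plans no change estimate anywhere for these assays, and the documents do not support that. The gap is that the SAP does not carry the protocol's rule into these sections.

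Third, a reader might infer that effects would be judged by whether the separate CIs overlap, and that real effects would usually be missed. Nothing in the documents plans such a rule. Any detection rate would rest on an effect size that they do not give, and for a large effect the two approaches would agree. No such rate is claimed here. The reading does not arise at all for anti-IIa, which has no planned CI and whose patient listing keeps the pairs visible.

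Fourth, a reader might infer that the 7-day summary will be empty and Day 30 unreported. If the entry is a mislabel of the Day 30 window, the data would appear under the wrong label instead. The listed over-time tables and time-course figures do not exclude Day 30 by their titles. Protocol 3.4.3 also sets TFPI evaluation through 72 hours, so the maintenance question does not depend on this sample.

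Finally, taking changes in patients with both samples matches the baseline to each visit, but the set of patients can still shift from one visit to the next. Showing the number of pairs makes this visible and does not remove it.

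**Conclusion.** The point holds as a minor one, in two parts. First, for TFPI, ATIII and anti-IIa the SAP gives level summaries where the objective is an effect. That is out of line with its own handling of free fraction and ETP and with protocol 11.7.4. Second, SAP 4.5.2, 4.5.4, 5.15.1.3 and 5.15.1.4 list a sampling time that Amendment 6 does not have and leave out one that it does: one of nine entries.

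The primary endpoints, their tests and the type I error are untouched. The gain in precision depends on the unknown correlation. Under equal SDs and an assumed rho of 0.3 to 0.7, the paired SE of a mean change is 0.84 to 0.55 times the unpaired SE. The mismatch in sampling times is judged against the Amendment 6 schedule, which the SAP says it follows; earlier schedules are not in the documents.

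**What to change.** - **SAP 5.15.1.3 and 5.15.1.4:** derive each patient's change and percent change from baseline at every post-dose time, in patients with both samples (the rule in SAP 5.9). Report the median change with the distribution-free 95% CI already specified in SAP 5.13.1, and the number of pairs at each time.
- **SAP 5.15.1.5:** add change and percent-change columns to the anti-IIa by-time table, on the same pairs.
- **Keep the level tables** as description.
- **SAP 4.5.2, 4.5.4, 5.15.1.3 and 5.15.1.4:** reconcile the 7-day entry with Appendix A, so that the scheduled Day 30 sample (window Days 30 to 37) is named and summarised.

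The cost is SAP wording and a few table columns from data already collected. The one small downside is that n in the change summaries will be slightly lower than in the level tables, since both samples are needed.

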5.15.1.4. Antithrombin III (ATIII)

For patients enrolled in Amendment 4, ATIII will be collected at baseline prior to and exanet treatment, EOI, 4, 8, 12, 24, 48, and 72 hours, and 7 days post and exanet treatment. Mean, median, standard deviation, minimum, and maximum value, and 95% CI for the median will be presented. Confidence intervals will be estimated using a distribution free procedure as described above for the primary efficacy analysis.

5.15.1.5. Anti-Factor IIa Activity

For enoxaparin patients, Anti-factor IIa levels (pre- and post-administration of andexanet will be collected. Outcome will be presented in a summary table for each time point and data listing by patient.

5.15.1.6. Hemostatic Efficacy in ICH Patients

Hemostatic efficacy following and examet treatment will be analyzed including all patients in the efficacy population with ICH bleeding type with valid EAC hemostatic efficacy adjudication. The proportion of patients in the Analysis Population who are adjudicated to have effective hemostasis (excellent or good) by the independent EAC will be summarized. An exact 95% CI will be reported. Analysis will be performed for the overall ICH patient population and by age category, sex, region, FXa Inhibitor., and and examet dose.

5.15.1.7. Use of Red Blood Cell Transfusions

The proportion of patients that received red blood cell transfusion after the start of andexanet treatment will be summarized for both the safety and efficacy populations. The proportion of patients that receive red blood cell transfusion and the Fisher exact 95% CI will be presented for the overall population, bleeding type, FXa inhibitor, andexanet manufacturing process and andexanet dose. In addition, the number of red blood cell units transfused per patient from the start of the andexanet bolus through 12 hours after the end of the andexanet infusion will be presented as data listing.

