11.5.4. Exploratory Efficacy Endpoints

The following additional efficacy endpoints will be analyzed as exploratory:

- The number of patients receiving one or more red blood cell transfusions from the start of the andexanet bolus through 12 hours after the end of andexanet infusion.
- For patients receiving apixaban, rivaroxaban, or edoxaban, to evaluate the decrease in free fraction of the FXa inhibitor following and examet administration.
- The number of red blood cell units transfused per patient from the start of the andexanet bolus through 12 hours after the end of the andexanet infusion.
- The use of non-study-prescribed blood products and/or hemostatic agents.
- The occurrence of re-bleeding following and examet treatment. Re-bleeding is defined as follows: recurrent bleeding from the same or another anatomical site, or new bleeding from a different anatomical site within 24 hours of initial and examet treatment and after achieving initial good/excellent hemostasis.
- Andexanet reversal of anticoagulant effect as measured through TG parameters (with, Endogenous Thrombin Potential [ETP] as the primary measure), for both the Tissue Factor (TF)-initiated assay and the non-TF-initiated assay.
- TFPI levels, both free and total, pre- and post-administration of andexanet.
- ATIII levels, pre- and post-administration of andexanet.
- Anti-factor IIa levels, pre- and post-administration of andexanet (enoxaparin patients only).
- The achievement of hemostatic efficacy in ICH patients at high risk of hematoma expansion.
- Change from baseline in GCS at 1 hour, 12 hours, and 30 days (for ICH patients only).
- Change from baseline in mRS at 1 hour, 12 hours, and 30 days (for ICH patients only).
- Change from baseline in NIHSS at 1 hour, 12 hours, and 30 days (for ICH patients only).

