Exploratory endpoints consisting of counts data will be summarized by observed rates and exact 95% CIs. Dichotomous data will be described analogously to the primary endpoint.

Further details of the analysis of the efficacy endpoints will be provided in the SAP.

11.5.7. Assessment of the Relationship Between Effective Hemostasis and Percent Decrease in Anti-fXa Activity

The following analyses are planned to further assess the relationship between hemostasis and decrease in anti-fXa activity:

Analysis of "Responders" (patients with a large percent decrease in anti-fXa activity) anchored to Hemostatic Efficacy. The percent decrease from baseline in anti-fXa activity in the evaluation period (relative to baseline) will be anchored to the achievement of hemostatic efficacy (i.e., the primary endpoint). This will be done calculating the median and mean percent decrease from baseline values for patients who achieved hemostatic efficacy and for patients who did not achieve hemostatic efficacy, with the expectation that those patients who achieved hemostatic efficacy had a greater mean and median percent decrease than those who did not.

Cumulative Distribution Function (CDF) Analysis. The CDF of change in anti-fXa activity for patients with and without benefit will be plotted. The horizontal axis will be the anti-fXa activity achieved (from 0-100%, and including negative values if any patient had an increase in anti-fXa activity), and the vertical axis will be the percent of patients with that level, or less, achieved. The two CDFs will be plotted on the same figure to allow comparisons. This enables visualization of percent with clinical benefit at every possible cut-point of percent decrease in anti-fXa activity.

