4.6.3. Use of Red Blood Cell Transfusions

• Were Blood Products and Hemostatic Agents used Post Treatment (yes, no)

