5.15.1.9. Re-Bleeding

Re-bleeding data will be listed with FXa inhibitor, initial bleeding type, and and exanet dose.

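### The SAP drops the 12-hour limit from the red-cell transfusion proportion and specifies only listings for red-cell units and re-bleeding

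*SAP*

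**What the plan says.** **Patients transfused.** Protocol 11.5.4, like the Synopsis, counts patients with one or more "red blood cell transfusions from the start of the andexanet bolus through 12 hours after the end of andexanet infusion". SAP 5.15.1.7 instead takes the proportion of patients "that received red blood cell transfusion after the start of andexanet treatment will be summarized" for the safety and efficacy populations, with an exact 95% interval. It gives no end time.

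**Units per patient.** This is a separate endpoint in Protocol 11.5.4, over the same 12-hour window. SAP 5.15.1.7 keeps the window, but the units from bolus start "through 12 hours after the end of the andexanet infusion will be presented as data listing".

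**Transfusion variable.** SAP 4.6.3 is headed as red-cell transfusion use. Its only item is "Were Blood Products and Hemostatic Agents used Post Treatment (yes, no".

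**Re-bleeding.** Protocol 11.5.4 makes its occurrence an exploratory efficacy endpoint, within 24 hours of initial treatment and after initial good or excellent hemostasis. SAP 4.6.4 defines an EAC-adjudicated yes/no variable. The whole analysis text in SAP 5.15.1.9 is "Re-bleeding data will be listed with FXa inhibitor", initial bleed type and andexanet dose.

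**Method.** Protocol 11.5.6 gives count endpoints observed rates with exact 95% intervals. For yes/no endpoints it says "Dichotomous data will be described analogously to the primary endpoint", that is, a proportion with a 95% interval.

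**The concern.** This is a single-arm study, so readers will set its rates beside rates from elsewhere, and the time window of each rate then matters. A red-cell transfusion given days later, for surgery, a new bleed or chronic anemia, says little about early bleeding control. Under the SAP wording it would still count if it was recorded.

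The missing limit is hard to read as shorthand, because the same SAP paragraph writes out the 12-hour window for units per patient. A programmer following the text literally would apply the window to the listing and not to the proportion.

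A listing shows individual cases. It gives no rate, interval or denominator. For re-bleeding the denominator is not obvious, since the definition requires that hemostasis was first achieved.

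**Working it through.** The plan states no figure for these endpoints, so there is none to reproduce. The check is a comparison of the texts, plus a scale for what cannot be sized.

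**1. Windows and outputs side by side**

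| Endpoint | Protocol window | SAP window | Protocol output (11.5.6) | SAP output |
|---|---|---|---|---|
| Patients transfused with red cells | bolus start to 12 h after end of infusion | from start of andexanet, no end | rate or proportion with 95% CI | proportion with exact 95% CI |
| Red-cell units per patient | same | same | observed rate with exact 95% CI | listing |
| Re-bleeding | within 24 h of initial treatment | same (4.6.4) | rate or proportion with 95% CI | listing |

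The first row differs in the window. The second and third differ in the output.

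**2. Size of the window effect**

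Let p12 be the proportion transfused by 12 hours after the infusion, and d the proportion first transfused later and recorded. Then:

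SAP proportion = p12 + d.

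The documents give neither term. Protocol 7.2.2 asks for the units, date and time of blood products without an end time. The Appendix A row for blood products cannot be read for its end. If recording stops at 12 hours, d = 0 and the two figures coincide.

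For scale only, assume p12 = 25% and take all 477 locked patients (SAP 1.0) as the denominator. That is 119 patients by 12 hours.

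| Assumed d (points) | SAP count | Extra patients | Exact 95% CI |
|---|---|---|---|
| 0 | 119 | 0 | 21.1–29.1% |
| 5 | 143 | 24 | 25.9–34.3% |
| 10 | 167 | 48 | 30.7–39.5% |
| 15 | 191 | 72 | 35.6–44.6% |

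The shift equals d by construction. The table says nothing about how large d is.

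**3. The 4.6.3 item**

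The item is neither limited to red cells nor given a window. Against it, SAP 5.15.1.7 names red cells for the proportion, and so do Tables 14.2.4.7a and 14.2.4.7b and Listing 16.2.6.5. Other products have their own section (5.15.1.8) and Listing 16.2.6.6. The variable section and the analysis section therefore disagree.

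**4. Re-bleeding**

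The only re-bleeding output named in the SAP is Listing 16.2.7.7.

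The primary endpoint does not fill the gap. Hemostatic efficacy is assessed to 12 hours after the end of infusion (Protocol 11.5.1). With a bolus of about 15–30 minutes and an infusion of about 120 minutes, that is 12 + 2.25 to 12 + 2.5 = 14.25 to 14.5 hours after bolus start. If the 24 hours run from bolus start, the last 24 − 14.5 = 9.5 to 24 − 14.25 = 9.75 hours of the re-bleeding window fall outside it.

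The denominator needs care. Protocol 11.5.1 rates a patient re-dosed for re-bleeding up to 12 hours as poor/none, and the SAP has no separate flag for initial hemostasis. Restricting the denominator to patients with a final good or excellent rating would remove those early re-bleeders and bias the proportion downward. All patients in a stated population is the safe denominator.

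An exact (Clopper–Pearson) interval for x events in n has lower limit Beta(0.025; x, n−x+1) and upper limit Beta(0.975; x+1, n−x). With n = 477 and assumed event counts:

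- 5 events: 1.0% (0.3–2.4)
- 10 events: 2.1% (1.0–3.8)
- 24 events: 5.0% (3.2–7.4)
- 48 events: 10.1% (7.5–13.1)

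Even a small count gives a usable upper bound.

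**5. Declaration**

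SAP 5.17.2 lists the main changes to the analysis plan: the Generation stratification, the broader thrombotic-event definition, urinary bleeds, the anti-fXa relationship analyses, and the earlier edoxaban and Japan updates. None concerns transfusion or re-bleeding.

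**The case against.** **All products would be counted.** A reader might infer from SAP 4.6.3 that platelets, plasma and hemostatic agents enter the red-cell proportion. The documents do not support this. Nothing says the proportion is derived from that item, and the analysis text, tables and listing all name red cells. What stands is a heading and item that do not match.

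**Re-bleeding will not be estimated at all.** A reader might infer this from 5.15.1.9. It goes too far. SAP 4.6.4 says its re-bleeding variables are to be analysed, and SAP 5.1 has a general rule that categorical variables get counts and percentages with 95% intervals. Listing 16.2.7.7 is titled a summary, and the table list is labelled as samples, so a missing table proves little. What stands is that the section specific to re-bleeding provides only a listing and names no denominator.

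**The window may not matter.** This is fair. If transfusions are recorded only to 12 hours, nothing changes. The SAP also keeps the window for units, so it has not abandoned it.

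**These endpoints are exploratory, and Protocol 11.5.6 leaves further detail to the SAP.** This is true and limits the weight of the point. Further detail does not extend to an undeclared change of window or output.

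**Conclusion.** The SAP's red-cell proportion has a wider window than the protocol endpoint. Red-cell units and re-bleeding are specified only as listings where the protocol calls for rates or proportions with 95% intervals. These departures are not declared in SAP 5.17.2. The 4.6.3 item is inconsistent with the red-cell analysis but does not show that other products would be counted.

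The numerical effect is not known from the documents. It equals the share of patients first transfused after 12 hours and recorded, which may be zero. The percentages and event counts shown above are assumptions for scale, as is the use of 477 as the denominator. The primary analysis and type I error are unaffected. This is a minor point, worth correcting because it is cheap.

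**What to change.** - **SAP 5.15.1.7:** end the window for the proportion at 12 hours after the end of the andexanet infusion, and summarise red-cell units per patient over the same window with an observed rate and exact 95% interval.
- **SAP 4.6.3:** make the item specific to red cells, with the same window.
- **SAP 5.15.1.9:** report the number and proportion of patients with EAC-adjudicated re-bleeding within 24 hours, with an exact 95% interval. Use all patients in a stated analysis population as the denominator (Listing 16.2.7.7 already uses the Safety Population), not only those with a final good or excellent rating.
- **SAP 5.17.2:** if the sponsor prefers any of the present choices, declare it there as a departure from the protocol.

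The cost is SAP wording and a few table rows. Protocol 7.2.2 already asks for transfused units with date and time, and SAP 4.6.4 already has the adjudicated re-bleeding variable with start time, so no new data are needed.
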